### 4.3. Removal of Patients from Therapy

Patients have the right to withdraw from the study at any time for any reason. The investigator has the right to withdraw patients from the study according to his/her discretion. When a patient discontinues treatment early, every effort will be made to conduct a post-treatment follow-up visit within 4 weeks after the last dose of study drug or prior to the initiation of new treatment. This post-treatment evaluation may be conducted over the phone if the patient is unable to return to the clinic. The reason(s) for withdrawal must be recorded.

Criteria for terminating participation in the study are listed below:

- Clinically significant progressive disease defined as > 50% increase in the percentage of blasts in bone marrow or peripheral blood over baseline to reach at least 20% blasts in bone marrow or peripheral blood by two assessments while on treatment with an adequate dose
- Lack of efficacy refers to treating physician's judgment that patients are unlikely to benefit from continuation of treatment despite not meeting the criterion of clinically significant progressive disease.
- Unacceptable toxicity
- Patient withdrawal of consent for treatment
- Investigator's discretion that it is in the best interest of the patient to withdraw
- Intercurrent illness: a condition, injury, or disease unrelated to cancer in the opinion of the investigator, that renders continuing sapacitabine treatment unsafe or regular follow-up impossible

- General or specific changes in the patient's condition that renders the patient ineligible for further treatment
- Noncompliance with study medication or protocol-required evaluations and followup visits
- Termination of the clinical trial by the sponsor

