	(1) For patients with pretreatment hemoglobin < 11 g/dL, >2g/dL increase in hemoglobin; for RBC transfusion - dependent patients, transfusion - independence*				
	(2) For patients with a pretreatment platelet count <100,000/mm³, an absolute increase of ≥30,000/mm³; for platelet transfusion-dependent patients, stabilization of platelet counts and platelet transfusion independence*.				
	(3) For patients with absolute neutrophil count (ANC) $< 1,500/$ mm  before therapy, $\ge 100\%$ increase, or an absolute increase $> 500/$ mm  , whichever is greater.				
	Minor response:				
	(1) For patients with pretreatment hemoglobin < 11 g/dL, 1-2 g/dl increase in hemoglobin; for RBC transfusion – dependent patients, 50% decrease in transfusion requirements.				
	(2) Platelet response: for patients with a pretreatment platelet count $<100,000/\text{mm}^3, \ge 50\%$ increase in platelet count with a net increase $>10,000/\text{mm}^3$ but $<30,000/\text{mm}^3$ .				
	(3) For patients with absolute neutrophil count (ANC) $< 1,500/$ mm  before therapy, $\ge 100\%$ increase, but absolute increase $< 500/$ mm  .				
Stable disease (SD)**	Failure to achieve at least HI, but no evidence of clinically significant progression for > 16 weeks.				

\*independent of transfusions or transfusion –dependence refer to no packed red blood cell transfusion for 2 weeks and no platelet transfusion for 1 week .

Transfusion requirements for each patient are defined as the number of weeks during which at least one transfusion for red blood cells (RBCs) or platelets is administered and the mean number of units of RBC and platelet transfusions administered per month.

CYCLACEL LTD CONFIDENTIAL 34 of 56

\*\* for Part 2, 3 and 4 of the study only

Clinical benefit is defined as the achievement of CR, CRp, PR, major HI or SD. The duration of clinical benefit is measured from the earliest time when the patient achieved CR, CRp, PR or major HI to the first date when the major HI is lost; if the patient only achieved SD, the duration of clinical benefit is measured from the date of randomization or registration to the first date when clinically significant progression of disease is observed.

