The duration of CR, CRp, PR or CRi or hematological improvement is measured from the time when response criteria are first met until the first date that recurrent or progressive disease is documented. To avoid premature discontinuation of patients who have had a temporary flare of the disease due to treatment interruptions, dose reductions, acute infection or other plausible explanations, a second assessment should be performed in these patients to confirm the recurrence or progression of disease.

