#### 11.4. Data Analysis

The intent-to-treat population for Part 1 of the study will include all patients who have received at least one dose of study drug on an assigned dosing schedule. The primary analysis population will consist of patients who underwent randomization. The primary and secondary efficacy endpoints will be analyzed separately within the AML or MDS stratum. Additional patients accrued to a dosing schedule that has produced at least 20% CR/CRi will be analyzed separately. The rate of 1-year survival and that of CR, CRp, PR CRi, or hematological improvement, will be reported with 95% confidence interval. The intent-totreat population for Part 2 of the study will include all patients who have received at least one dose of the study drug. The rate of clinical benefit response (CR, CRp, PR, major HI or SD) and the rate of CR/CRp with be reported with 97.5% confidence interval. The intent-to-treat population for Part 3 and 4 of the study will include all patients who have received at least one dose of study drug on an assigned dosing schedule. The primary analysis population will consist of patients who underwent randomization. Additional patients accrued to a dosing schedule that has produced at least 20% clinical benefit response rate will be analyzed separately. Duration of CR, CRp, PR, CRi, HI, SD and overall survival will be estimated using the method of Kaplan and Meier. Patients who are discontinued from the study for reasons other than progression of disease will be censored at the time of the last response evaluation. The median number of transfusion-free weeks will be calculated for the 8 weeks

immediately prior to the first dose of study drug and while on study. For patients who required at least one transfusion of RBC or platelet within the 8 weeks immediately prior to the first dose of study drug, there will be a calculation of those who have achieved at least a 50% increase in the number of transfusion-free weeks on study over these at baseline, i.e., during the 8 weeks immediately prior to the receiving the first dose of the study drug.

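### Censoring every non-progression exit in the duration curves, lack of efficacy included and death by inference, makes responses and stable disease look longer than they are

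*Combined protocol and SAP*

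**What the plan says.** Section 11.4 (Data Analysis) names the curves: "Duration of CR, CRp, PR, CRi, HI, SD and overall survival will be estimated using the method of Kaplan and Meier". The next sentence gives the censoring rule: anyone who leaves for a reason other than progression is "censored at the time of the last response evaluation". It has no exceptions, and no competing-risk or sensitivity analysis is planned.

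Section 9 (Efficacy Assessment) defines what ends each duration:

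- CR, CRp, PR, CRi and HI run "until the first date that recurrent or progressive disease is documented".
- Clinical benefit in a responder runs "to the first date when the major HI is lost".
- Clinical benefit in a patient with stable disease only ends at clinically significant progression.

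None of these definitions mentions death.

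Section 4.3 sets the progression criterion for leaving: a rise of more than 50% in the blast percentage from its baseline value, "to reach at least 20% blasts in bone marrow or peripheral blood by two assessments while on treatment with an adequate dose". A separate reason on the same list, lack of efficacy, applies when the treating physician judges as follows: "patients are unlikely to benefit from continuation of treatment despite not meeting the criterion of clinically significant progressive disease".

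Section 9 makes the durations secondary efficacy endpoints in all four Parts.

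**The concern.** Kaplan-Meier censoring is harmless when those censored have the same outlook as those still followed. Two groups caught by this rule do not. A patient removed because the physician sees no further benefit is leaving because disease control is failing. A patient who dies in response has no further response to observe. If both are treated as open-ended, the curve credits them with time that they will not have, and the reported duration is too long.

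At stake is the reading of the secondary duration endpoints. They are not idle figures: Section 3.3 cites the longest response durations, together with the CR/CRp rate and the 30-day death rate, when it explains the 3-day schedule taken forward to Part 2.

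**Working it through.** The plan states no median, event count or precision for any duration, so there is no figure to reproduce. The check is a comparison of the text followed by two illustrations with assumed rates.

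**1. What the text does to each type of exit**

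- *Lack of efficacy, stable disease only.* Section 9 ends the duration at clinically significant progression. Section 4.3 defines lack of efficacy as not meeting that criterion. The exit is therefore never an event and is always censored. This is the clearest case.
- *Lack of efficacy after a response.* Suppose a CR patient's marrow blasts return above the 5% limit of Table 6 but stay below 20%, and the physician stops treatment. If this is documented as recurrence, Section 9 counts an event. Section 11.4, read literally, censors the patient because the recorded reason is not progression. The two sections conflict.
- *Death in response.* Neither section names it. Section 9 provides no event for it, and Section 11.4 covers all reasons other than progression, so censoring follows by inference.
- *Exits unrelated to prognosis*, such as pure withdrawal of consent. These need not bias the curve.

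**2. Death censored against death counted**

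Assumptions: independent constant hazards; median time to relapse m = 6 months; a share s of endings are deaths without progression. The documents give neither m nor s.

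- Relapse hazard: λ = ln 2 / m.
- Hazard of death without relapse: λ·s/(1−s).
- Median with deaths censored: m.
- Median to relapse or death: ln 2 / [λ + λ·s/(1−s)] = m(1−s).
- Ratio: 1/(1−s).

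| s | Deaths censored (months) | Relapse or death (months) | Ratio |
|---|---|---|---|
| 10% | 6.0 | 5.4 | 1.11 |
| 20% | 6.0 | 4.8 | 1.25 |
| 30% | 6.0 | 4.2 | 1.43 |
| 40% | 6.0 | 3.6 | 1.67 |

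The ratio does not depend on m; relapse medians of 4 and 9 months give the same factors.

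**3. Lack-of-efficacy exits**

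Simulation of 200,000 responders with exponential relapse times (median 6 months), monthly evaluations and no deaths. A share q is removed just before relapse would be documented and is censored at the last evaluation. The true median is 6.0 months.

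| q | Median under the rule (months) | Ratio to 6.0 |
|---|---|---|
| 10% | 6.6 | 1.1 |
| 20% | 7.4 | 1.2 |
| 30% | 8.4 | 1.4 |

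Here the target, time to relapse, is the same in both columns, so the excess is bias from informative censoring. The timing of removal is an assumption chosen to show the mechanism.

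**The case against.** Several points on the other side are sound.

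- Death appears neither in the censoring sentence nor in the Section 4.3 list of reasons for leaving. At its narrowest, the text leaves death in response unspecified. This stands, and so death is treated here as an inference.
- Section 9 defines duration by relapse. With independent hazards, censoring deaths recovers that relapse-time distribution, so the factors in step 2 compare two estimands and do not measure an error against the plan's own definition. This stands. A relapse-only curve still describes a setting in which nobody dies first, and readers will not take a reported duration that way.
- A patient still in CR is an unlikely lack-of-efficacy exit, and clinical benefit in responders ends at loss of major HI. This narrows the lack-of-efficacy problem mainly to stable disease and to the conflict in step 1.
- Marrow after later cycles is done as clinically indicated (Table 5, note h), but worsening counts are an example of such an indication, and blood counts are taken on Day 1 of each cycle. The documents do not show that many ends of response would be missed.
- Lack of efficacy is an open-label judgment by the treating physician. Making it a primary event would bring that subjectivity into the endpoint, so it belongs in a sensitivity analysis.

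A reader might also infer that longer durations will favour the more toxic schedule. The documents do not support this. Sections 11.1.2 and 11.3.2 select on observed 1-year survival, assuming similar toxicity, and duration enters no screening or selection rule. Deaths and the 14-day and 30-day mortality rates are reported separately.

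**Conclusion.** The concern holds for the secondary duration endpoints. Followed literally, Section 11.4 censors exits that reflect failing disease control, censors death in response by inference, and contradicts Section 9 where recurrence precedes a non-progression exit. Durations are overstated as a description of how long response or disease control lasts. The conflict between the sections needs no assumed rate.

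The size cannot be derived from the documents. The factor of 1.11 to 1.67 rests on constant independent hazards and an assumed 10% to 40% of endings being deaths without progression. The factor of about 1.1 to 1.4 rests on 10% to 30% leaving for lack of efficacy just before relapse. The only nearby figure, 10% all-cause death within 30 days on one Part 1 schedule (Section 3.3), covers all patients on that schedule and is not a rate of death in response.

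A reader might infer that the primary endpoint of Parts 1, 3 and 4 is distorted as well. Section 9 defines it for Part 1 as the proportion alive at 1 year from randomization, and Section 11.3 also measures it from randomization, so it does not pass through these duration curves. However, the censoring sentence directly follows one that also names overall survival and does not limit its own scope. That is an ambiguity to close; it does not show that survival will be censored this way.

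**What to change.** Amend Section 11.4 as follows:

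- (a) Count any documented recurrence or progression as an event, whatever reason for leaving is recorded, in line with Section 9.
- (b) Count death without prior progression as an event. If relapse alone is the target, report its cumulative incidence with death as a competing event. In either case, state a limit for deaths long after the last response evaluation: response status is then unknown, and an event placed at the death date could itself lengthen the duration.
- (c) Add a sensitivity analysis that counts lack-of-efficacy exits as events, chiefly for stable disease.
- (d) Confine the censoring sentence to the duration endpoints, so that it does not apply to overall survival.

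Align the Section 9 definitions with (b). Death dates are already needed for 1-year survival in Parts 1, 3 and 4 and for overall survival in Part 2, so no new data are required. The cost is a little more analysis work and somewhat shorter reported median durations.

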#### 3. STUDY DESIGN

### 3.1. Overall Study Design and Plan

Part 1: This is an open label, randomized, phase II study. Patients will be entered into two separate strata, AML or MDS, and randomized 1:1:1 to receive one of the following 3 dosing schedules within each stratum:

7-day low dose (Arm A): 200 mg b.i.d. x 7 consecutive days every 4 weeks

7-day high dose (Arm B): 300 mg b.i.d. x 7 consecutive days every 4 weeks

3-day high dose (Arm C): 400 mg b.i.d. x 3 consecutive days per week for 2 weeks every 4 weeks

AML patients will be stratified by previously untreated vs. treated for AML within the AML stratum.

Part 2: This is an open-label, single arm, phase II study. Patients will receive sapacitabine at 300 mg *b.i.d.* x 3 consecutive days per week for 2 weeks every 4 weeks.

Part 3: This is an open label, randomized, phase II study. Patients will be randomized 1:1:1 to receive one of the following 3 dosing schedules and the randomization will be stratified by prior treatment with decitabine for MDS (Yes or No):

Arm D: 200 mg b.i.d. x 7 consecutive days every 4 weeks

Arm E: 300 mg q.d. x 7 consecutive days every 4 weeks

Arm F: 300 mg b.i.d. x 3 consecutive days per week for 2 weeks every 4 weeks

Part 4: Eligible patients will be randomized to receive one of the following 3 dosing schedule and the randomization will be stratified by prior treatment with decitabine for MDS (Yes or No):

Arm G: 200 mg b.i.d. x 7 consecutive days every 4 weeks

Arm H: 300 mg q.d. x 7 consecutive days every 4 weeks

Arm I: 100 mg q.d. x 5 consecutive days per week for 2 weeks every 4 weeks

Treatment will continue until: clinically significant progressive disease; lack of efficacy; unacceptable toxicity; patient withdrawal of consent; investigator's discretion that it is in the best interest of the patient to withdraw; intercurrent illness or changes in patient's condition that renders patient ineligible, or continuing treatment of sapacitabine unsafe, or regular

follow-up impossible; non-compliance with study medication or protocol-required evaluations and follow-up; or termination of the clinical trial by the sponsor.

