#### 6.3. Duration of Treatment

Patients may continue treatment at the discretion of the treating physician until they meet the criteria for terminating participation in the study (Section 4.3).

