#### 7. STUDY CALENDAR

All procedures and evaluations may be performed within  $\pm$  3 calendar days of that specified in the protocol to accommodate patient convenience and scheduling. Patient consent must be obtained prior to any study-specific procedures.

Table 5 Study Flow Chart

Procedure	Pre- Study c	Cycle 1 (Day 1±3 d)	Cycle 1 (Day 8 ± 3d)	Cycle 1 (Day 15 ±3d)	Cycle 2 and subsequent cycles (Day 1 ± 3d)	Post-treatment follow-up i
Sapacitabine administration		X f			X	
Informed consent	X					
Medical history	X					
Concomitant meds	X	X g	X	X	X	X
Capsule count					X	
Physical exam in clinic (including vital signs and performance status)	X	Xg	X	Х	X g	X
Height	X					
Weight	X				X	X
CBCa	X	X g	X	X	X	X
Chemistry panel b	Х	X g	X		X	X
INR	X					
Transfusion requirements	X d		X	X	X	X
Number of hospitalized days	Xe		Х	Х	Х	X
Bone marrow aspirate and/or biopsy	Х				X h	
Bone marrow cytogenetics	X e					
Pulmonary function test of FEV1 and DLco	X e					
ECG	X		Х	X		X
Adverse events assessment			X	X	X	X
Chest x-ray (PA and Lateral)	X					

a: Differential of WBC will be done if WBC ≥ 300/µL

CYCLACEL LTD CONFIDENTIAL 29 of 56

b: Albumin, alkaline phosphatase, total bilirubin, bicarbonate, blood urea nitrogen, calcium, chloride, creatinine, glucose, lactic dehydrogenase, phosphorus, potassium, total protein, SGPT[ALT], SGOP (AST), sodium, uric acid

c: Within 2 weeks of the first dose of study drug except bone marrow cytogenetics which will be performed within 3 months (all patients) and pulmonary function test of forced expiratory volume in 1 second (FEV1) and lung diffusion capacity of carbon monoxide (DLco) which will be performed within 28 days prior to the first dose of the study drug as clinically indicated (Part 2 and 3 only); informed consent form may be obtained > 2 weeks prior to the first dose of drug but must be obtained prior to conducting any study-specific procedures

d: Transfusion requirements during the 8 weeks immediately prior to the first dose of study drug

e: Number of hospitalized days during the 8 weeks immediately prior to the first dose of study drug

f: The first dose of study drug must be administered within 7 days of randomization; sapacitabine may be dispensed at pre-study visit if the pre-study visit is within 7 days of the first dose of the study drug

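### The 50% rule for transfusion-free weeks sets an open-ended on-study count against a fixed 8-week baseline, so a patient with 1 to 7 free baseline weeks and an unchanged rate is expected to meet it at 12 to 16 weeks

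*Combined protocol and SAP*

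**What the plan says.** Transfusion requirements are a secondary endpoint in all four parts (Sections 2 and 9). Section 9 gives them two components. One is a count of weeks, "defined as the number of weeks during which at least one transfusion for red blood cells (RBCs) or platelets is administered". The other is "the mean number of units of RBC and platelet transfusions administered per month".

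Section 11.4 adds two summaries of transfusion-free weeks:

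- **A median.** "The median number of transfusion-free weeks will be calculated for the 8 weeks" before first dose, and also for the time on study.
- **A responder rule.** It applies to patients with at least one RBC or platelet transfusion in the 8 baseline weeks, and counts those who have "achieved at least a 50% increase in the number of transfusion-free weeks on study over these at baseline". Baseline is explained as "during the 8 weeks immediately prior to the receiving the first dose of the study drug". Footnote d of Table 5 uses the same window: "Transfusion requirements during the 8 weeks immediately prior to the first dose of study drug".

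Time on study is open-ended. Section 3.1 says "Treatment will continue until: clinically significant progressive disease; lack of efficacy; unacceptable toxicity" or another listed reason applies. Section 6.3 says "Patients may continue treatment at the discretion of the treating physician until they meet the criteria for terminating participation in the study". Nothing in the plan caps the on-study window for the transfusion summaries, matches it to 8 weeks, or divides the count by weeks observed.

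**The concern.** The rule compares a count out of 8 with a count out of however many weeks the patient stays. The second count can only grow with time. The rule therefore rewards length of stay, whether or not transfusion need has changed, and penalises short stays.

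Parts 1, 3 and 4 each set three schedules side by side. A schedule on which patients stay longer would tend to show more improved patients even if nobody's transfusion need had changed. The median of transfusion-free weeks and the Section 9 count of transfused weeks have the same unequal windows. The units-per-month measure is scaled by time and is not affected.

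**Working it through.** The plan states no expected rate for this rule, so there is no document figure to reproduce.

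**Inputs from the plan.** Baseline window 8 weeks and threshold a 50% increase in the number of free weeks (Section 11.4). At least one baseline transfusion is required, so free baseline weeks *b* run from 0 to 7 (Section 11.4). One cycle is 4 weeks (Section 6.1). Stable disease requires more than 16 weeks without clinically significant progression (Table 6), so stays beyond 16 weeks are foreseen.

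**Step 1: when an unchanged patient qualifies.** The patient needs ceil(1.5*b*) free weeks. At an unchanged weekly rate of *b*/8, the expected time is ceil(1.5*b*) ÷ (*b*/8). The last three columns give the chance of having qualified, taking weeks as independent: P[Binomial(*n*, *b*/8) ≥ ceil(1.5*b*)].

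| *b* | Free weeks needed | Expected week | By week 12 | By week 16 | By week 24 |
|---|---|---|---|---|---|
| 1 | 2 | 16.0 | 0.453 | 0.612 | 0.820 |
| 2 | 3 | 12.0 | 0.609 | 0.803 | 0.960 |
| 3 | 5 | 13.3 | 0.490 | 0.777 | 0.976 |
| 4 | 6 | 12.0 | 0.613 | 0.895 | 0.997 |
| 5 | 8 | 12.8 | 0.510 | 0.900 | 0.999 |
| 6 | 9 | 12.0 | 0.649 | 0.973 | 1.000 |
| 7 | 11 | 12.6 | 0.547 | 0.990 | 1.000 |

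The expected time is 12 to 16 weeks, or 3 to 4 cycles. Qualifying by week 16 is certain only if the baseline pattern repeats exactly, because then 2*b* ≥ ceil(1.5*b*).

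**Step 2: errors in both directions.**

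- *Worse, but called improved.* Transfused in 4 of 8 weeks (50%), then in 10 of 16 (62.5%). Free weeks go from 4 to 16 − 10 = 6, and 6/4 = 1.5.
- *Better, but not called improved.* With *b* = 6 or 7, 9 or 11 free weeks are needed, so a patient who stops needing transfusions altogether cannot qualify within 8 weeks.
- *Undefined.* With *b* = 0 there is no percentage increase, and no rule is given.

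**Step 3: illustrative no-change model.** The documents give no transfusion rates, so these are assumptions. Each week is free with probability *q*, and consecutive weeks have correlation *r*: P(free after free) = *q* + *r*(1 − *q*), and P(free after transfused) = *q*(1 − *r*). On-study weeks continue from baseline, patients have at least one transfused baseline week, and *b* = 0 counts as not improved. Proportion called improved by weeks on study:

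| *r* | *q* | As written: 4 / 8 / 16 / 24 weeks | Divided by weeks observed: 4 / 8 / 16 / 24 weeks |
|---|---|---|---|
| 0 | 0.3 | 0.094 / 0.296 / 0.649 / 0.844 | 0.287 / 0.296 / 0.285 / 0.258 |
| 0 | 0.5 | 0.056 / 0.245 / 0.777 / 0.971 | 0.273 / 0.245 / 0.228 / 0.195 |
| 0 | 0.7 | 0.008 / 0.147 / 0.898 / 0.999 | 0.202 / 0.147 / 0.130 / 0.114 |
| 0.6 | 0.3 | 0.085 / 0.193 / 0.368 / 0.494 | 0.202 / 0.193 / 0.193 / 0.176 |
| 0.6 | 0.5 | 0.099 / 0.282 / 0.599 / 0.768 | 0.292 / 0.282 / 0.279 / 0.262 |
| 0.6 | 0.7 | 0.074 / 0.300 / 0.787 / 0.925 | 0.314 / 0.300 / 0.298 / 0.279 |

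**Step 4: a patient who truly worsens.** If the free share halves from 50% to 25% (*r* = 0), the rule as written calls 53% of such patients improved at 24 weeks. Divided by weeks observed, it calls 4%.

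**The case against.** The strongest reply is that this is one descriptive table. Futility, activity, toxicity and selection decisions (Sections 11.1 to 11.3) rest on response, serious adverse events, 30-day death and 1-year survival. The same endpoint already has a time-scaled component in units per month. This stands, and it limits the weight of the point.

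Second, the 12-to-16-week figure takes the observed baseline rate as the true one and excludes *b* = 0. If *b* is instead a random draw from a fixed true rate, the expected crossing is 11.5 to 14.4 weeks for true free shares of 0.875 down to 0.25, but 21 weeks at 0.125. In the clustered case with *q* = 0.3, under half have qualified even by week 24. Part of that comes from the 29.5% with *b* = 0. Among the rest the figures are 0.368/0.705 = 52% at 16 weeks and 0.494/0.705 = 70% at 24 weeks. The range needs its conditions stated, but the growth with time remains in every case examined.

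Third, dividing by weeks observed is not perfect. With independent weeks and *q* of 0.5 or 0.7, the proportion falls with stay (0.273 to 0.195 and 0.202 to 0.114 from week 4 to week 24), a tilt towards short stays. It is much smaller than the rise under the rule as written, and slight when weeks are clustered.

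Finally, the sponsor may have meant a rate or a matched window. The text does not say so. If that was the intent, the change is a clarification.

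**Conclusion.** The rule is wrong as written. It sets unequal lengths of time against each other and can label a patient with a rising transfusion burden as improved. That follows from the wording alone: 1.5 × 8 = 12 weeks, and 4 of 8 then 10 of 16. The 12-to-16-week range holds for patients with 1 to 7 free baseline weeks whose on-study rate equals their baseline rate.

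The modelled proportions rest on assumed values of *q* and *r*. From 8 to 24 weeks on study they rise to between 49% and over 99% with no change in need. The documents give neither transfusion rates nor lengths of stay, so the size of any distortion between schedules is unknown. The primary endpoints and all go/no-go rules are unaffected. The definition should be corrected before the transfusion results are analysed.

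**What to change.** In Section 11.4, compare equal time and keep the plan's unit. Choose one basis:

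- **(a)** the share of observed on-study weeks that were transfusion-free, against the share in the 8 baseline weeks, with weeks observed reported by schedule; or
- **(b)** free weeks in the first 8 weeks from first dose, against the 8 weeks before it.

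Report the median on the same basis, and give the Section 9 count of transfused weeks a denominator.

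State in advance how these patients are classified: 0 free baseline weeks (no percentage exists); 6 or 7 free baseline weeks (a 50% increase would need a share of 1.125 or 1.3125, which is impossible under either basis); and those who die or leave before 8 weeks. These groups can be large. In the model, 6 or 7 free weeks covers 1%, 14% and 52% of the subgroup at *q* = 0.3, 0.5 and 0.7 (clustered 9%, 23% and 41%).

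One option that is defined for every patient in the subgroup is at least a 50% decrease in transfused weeks between the two 8-week windows, with early leavers counted as not improved. It does not depend on stay beyond 8 weeks, but it calls 4%, 14% and 28% of unchanged patients improved (clustered 17%, 30% and 46%). At *q* = 0.7 that exceeds the rule as written at 8 weeks (15%; clustered 30%).

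Trade-offs: (b) and the option will probably lower the reported rate for short stays, and they cover a period that includes early myelosuppression, so later improvement shows only under (a). Very short stays make (a) imprecise and tilt it slightly upwards.

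The cost is a wording change. Table 5 already collects transfusions for the 8 baseline weeks and on study.
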